5.2. Secondary Objectives

The secondary objective of the study is to evaluate the efficacy of TNX-102 SL taken daily at bedtime over an additional 12 weeks in patients with PTSD who have completed a double-blind lead-in study.

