6.3.2. Efficacy

Descriptive statistics by treatment group and study visit will be displayed for a number of efficacy endpoints including:

- Change from both baselines in the total CAPS-5 score
- Proportion of patients with a CGI-I score of “very much improved” or “much improved” from both baselines
- Change from both baselines in the SDS total score
- Change from both baselines in the individual items assessed using the SDS
- Change from both baselines in patients’ quality of sleep using the PROMIS Sleep Disturbance scale
- Change from both baselines in CAPS-5 symptom cluster subscores
- Proportion of patients with a $\geq 50\%$ improvement from baseline (both baselines) in total CAPS-5 score
- Change from both baselines in BDI-II score

Hypothesis testing will also be performed on the above efficacy endpoints. Missing values will not be imputed, and no adjustments will be made for multiplicity.

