12.5. Exploratory Analyses

Efficacy results for the CAPS-5 will be compared between the patients who were treated with TNX-102 SL and those treated with placebo during the double-blind lead-in study.

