3.2 Method of Treatment Assignment and Randomization

All patients will be assigned to TNX-102 SL, 5.6 mg regardless of which treatment arm they were randomized to in the lead-in study. No patients or site personnel will know what the prior treatment was in the double-blind lead-in study.

Throughout this document, when describing analyses performed by treatment group, this will refer to the treatment that the subject was randomized to in the double-blind lead-in study.

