7.2.1 Clinician-Administered PTSD Scale for DSM-5 (CAPS-5)

The primary efficacy endpoint is the change from baseline in total CAPS-5 score at Week 12 (Visit 6).

The CAPS-5 is an updated and validated version of a semi-structured interview that has been designed to assess the essential features of PTSD as defined by the DSM-5 ([Weathers et al, 2013](#)). The CAPS-5 affords the clinician flexibility to inquire about symptoms and diagnostic status over different time frames, such as past week, past month, and/or worst month for lifetime. For this study, a “Diagnostic” version of the CAPS-5 (past month recall) will be utilized at the Screening visit to confirm the diagnosis of PTSD and determine eligibility. A “Symptom Severity” version of the CAPS-5 (past week recall) will be completed by the clinician at all other time points (Baseline [Visit 2] and after 12 weeks of treatment [Visits 6]).

The CAPS-5 interview contains the following components

- Life Events Checklist for DSM-5 (LEC-5): Completed by the participant at the Screening Visit (Visit 1 only)
- Criterion A – Assessment Form (CA-AF): this semi-structured interview is based on the Criterion A discussion included in the CAPS-5, but modified (by [name], CAPS-5 lead author) specifically for this study to ensure sufficient review of the traumas outlined on the participant-completed LEC-5 and to capture clear description of the participant’s index/qualifying trauma (Visit 1 only)
- PTSD symptoms, onset/duration, distress/impairment, global rating, and dissociative symptoms:
 - Criterion B: Items 1-5 (Intrusion symptoms)
 - Criterion C: Items 6-7 (Avoidance symptoms)
 - Criterion D: Items 8-14 (Negative alterations in cognitions & mood)
 - Criterion E: Items 15-20 (Arousal and reactivity symptoms)
 - Criterion F: Items 21-22 (Onset and duration of symptoms)
 - Criterion G: Items 23-25 (Distress and impairment due to PTSD)
 - Global ratings: Items 26-27 (Validity, severity)
 - Dissociative symptoms: Items 29 (Depersonalization) and 30 (Derealization)

In addition to the total symptom score (obtained from the sum of Criteria B-E), the CAPS-5 affords the opportunity to examine clusters of symptoms, including Criterion B

(intrusion symptoms), Criterion C (persistent avoidance), Criterion D (negative cognitions and mood), and Criterion E (arousal and reactivity), all of which will be secondary efficacy endpoints.

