7.2.2 Clinician Global Impression of Improvement (CGI-I)

The CGI-I will be completed by an Investigator to evaluate the participant's status since initiation of treatment. The CGI-I, status since initiation of treatment, is the first key secondary efficacy endpoint in this study. The CGI-I should be completed toward the end of each in-clinic post-Baseline study visit once all other assessments are available for the investigator's review. Once the participant has been randomized, an Investigator completes the CGI-I assessment after 4, 8, and 12 weeks of treatment in order to assess the overall change in the participant's status and answer the following question:

Since the initiation of treatment at Visit 2, the participant is:

- 1 = Very much improved
- 2 = Much improved
- 3 = Minimally improved
- 4 = No change
- 5 = Minimally worse
- 6 = Much worse
- 7 = Very much worse

The key secondary analysis of CGI will treat it as a continuous variable (scored 1-7 as above). There will be an additional outcome presented where a responder on the CGI-I is defined a participant who is scored as 'Very much improved' or 'Much improved' and compared between the study arms.

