9.1.1 Efficacy Analysis Model

Continuous endpoints collected at baseline and Week 12 will be analyzed in an analysis of covariance model (ANCOVA) for the change from each baseline (P301 baseline and P303 baseline) in separate, independent models. The model will include all participants in the safety population, and the dependent variable will be the observed change from each baseline to Week 12. Covariates in the model will include the fixed categorical effects of treatment, site, sex, current tobacco use status, presence of current MDE, as well as the continuous fixed covariate of baseline score.

The least squares means and 95% confidence intervals (CIs) will be calculated for the treatment difference between the subjects that received TNX-102 SL and placebo in the lead-in study at each time point.

Endpoints reported in this manner will include:

- CAPS-5 Total Score
- Change from baseline in SDS total.
- Change from baseline in participants' quality of sleep using the PROMIS Sleep Disturbance scale.
- Change from baseline in the disruption of work/school activities assessed using the SDS.
- Change from baseline in disruption of social life/ leisure activities assessed using the SDS.
- Change from baseline in the disruption of family life/home responsibilities assessed using the SDS.
- Change from baseline in CAPS-5 Arousal and Reactivity (Criterion E).
- Change from baseline in CAPS-5 Intrusion symptoms (Criterion B).
- Change from baseline in CAPS-5 Negative Cognition and Mood (Criterion D).
- Change from baseline in CAPS-5 Persistent Avoidance (Criterion C).
- Change from baseline in CAPS-5 Sleep Disturbance (item E-6).
- Change from baseline in CAPS-5 Exaggerated Startle (item E-4).
- Change from baseline in CAPS-5 Reckless or Self-Destructive Behavior (item E-2).
- Change from baseline in CAPS-5 Depersonalization (item 29).
- Change from baseline in CAPS-5 Derealization (item 30).

The change from baseline in BDI-II score will be analyzed in a Mixed Model Repeated Measures (MMRM) for the change from each baseline (P301 baseline and P303 baseline)

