9.1.2 Categorical outcomes

Binary data over time will be analyzed using a Cochran Mantel Haenszel (CMH) test stratified by presence of current major depressive episode. Participants with missing data will be analyzed as though they are non-responders. This will be reported for each endpoint. Differences in proportions along with two-sided 95% CIs will also be reported. Two-sided p-values for the test of no difference between the treatment groups will be provided.

These endpoints will include:

- Proportion of participants with a CGI-I score of “much improved” or “very much improved”.
- Proportion of participants with a $\geq 50\%$ improvement from baseline in Total CAPS-5 score.

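### Every efficacy p-value in the SAP compares the former lead-in arms while both take TNX-102 SL, so none tests efficacy over the additional 12 weeks

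*SAP*

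**What the plan says.** **Objective.** Protocol 5.2 sets out to "evaluate the efficacy of TNX-102 SL taken daily at bedtime over an additional 12 weeks". Protocol 6.3.2 adds that "Hypothesis testing will also be performed on the above efficacy endpoints", without naming a null hypothesis or a contrast. SAP 2.1.2 gives a safety objective in place of the efficacy one, so the SAP does not say which question its efficacy p-values answer.

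**Treatment.** SAP 3.2: "All patients will be assigned to TNX-102 SL, 5.6 mg regardless of which treatment arm they were randomized to in the lead-in study". The same section defines treatment group, throughout the SAP, as the lead-in randomised arm.

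**Tests.** SAP 9.1.1 estimates "the treatment difference between the subjects that received TNX-102 SL and placebo in the lead-in study at each time point", with p-values between arms at each visit. It fits separate models for change from the P301 and the P303 baseline, each adjusted for the matching baseline score. The method is ANCOVA for endpoints measured at baseline and Week 12, and MMRM for BDI-II and CGI-I. For the responder endpoints SAP 9.1.2 uses a CMH test: "Two-sided p-values for the test of no difference between the treatment groups will be provided".

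**Labels.** SAP 7.2.1 makes CAPS-5 change the main efficacy endpoint: "The primary efficacy endpoint is the change from baseline in total CAPS-5 score at Week 12 (Visit 6". SAP 7.2.2 gives CGI-I the next rank: "The key secondary analysis of CGI will treat it as a continuous variable (scored 1-7 as above". Protocol 12.5, headed Exploratory Analyses, is the only place where the protocol spells out a former-arm comparison: "Efficacy results for the CAPS-5 will be compared between the patients who were treated with TNX-102 SL and those treated with placebo".

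**Within-arm change.** Protocol 12.2 plans descriptive statistics by former arm and for all patients, and SAP 9.1.1 adds LS means and SEs. SAP 2.2.1 speaks of comparisons with both baselines but refers to SAP 7.1, which defines change and names no test. Confidence intervals for change from baseline are specified for laboratory values and vital signs (SAP 10.2, 10.4), not for efficacy.

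**The concern.** In a placebo-controlled trial, a difference between arms tests efficacy. In this extension both arms receive the same open-label drug, so the null hypothesis is that prior treatment makes no difference now. That is a legitimate question about early versus delayed start, but it is not the stated objective.

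The risk lies in how the results are read. SAP section 1 allows them into clinical study reports, submissions and manuscripts. A significant P301-baseline difference under a primary efficacy label could be reported as efficacy in the extension when it only carries the lead-in result forward. Conversely, if former-placebo patients benefit and catch up, the same table can look like no efficacy, or like loss of effect in the continuing arm.

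**Working it through.** **1. Count of efficacy p-values** (SAP 9.1.1 and 9.1.2; post-baseline visits at Weeks 4, 8 and 12)

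| Endpoints | Count |
|---|---|
| 15 ANCOVA endpoints × 2 baselines | 30 |
| BDI-II: 3 visits × 2 | 6 |
| CGI-I score: 3 visits × 2 | 6 |
| CGI-I responder: 3 visits × 2 | 6 |
| CAPS-5 responder: 1 visit × 2 | 2 |
| Total | 50 |

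The total is 44 if CGI-I has only one reference point. All are former-arm contrasts; none tests change during the extension.

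**2. What each contrast estimates.** Take lower scores as better and TNX/TNX minus Placebo/TNX as the contrast, so negative favours TNX/TNX. Let d be the lead-in benefit, g the extension gain common to both arms, c the extra extension gain in former-placebo patients, and b the within-arm slope of the final score on the P303-baseline score.

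- P301 baseline: (−d − g) − (−g − c) = −(d − c)
- P303 baseline, raw change: −g − (−g − c) = +c
- P303 baseline, ANCOVA: the arms differ by −d on the covariate and change has slope b − 1 on it, so the contrast is c − (b − 1)(−d) = c − (1 − b)d

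The common gain g appears in none of them. The ANCOVA offset (1 − b)d arises because the P303 baseline is a post-randomisation value already affected by the lead-in arm.

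**3. Size.** The documents give no N, SD, effect size or correlation, so there is no planned figure to reproduce. Assumptions: SD 1; correlations 0.5 (P301 with P303 baseline), 0.4 (P301 baseline with final) and 0.6 (P303 baseline with final, so b = 0.6); no dropout; two-sided 5%; only the matching baseline as covariate.

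Worked case, n = 80 per former arm, d = 0.4:

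- SE, P301 model: √(1 − 0.4²) × √(2/80) = 0.917 × 0.158 = 0.145
- SE, P303 model: √(1 − 0.6²) × √(2/80 + 0.4²/158) = 0.8 × 0.161 = 0.129

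| Scenario | P301 contrast | Significant | P303 ANCOVA contrast | Significant |
|---|---|---|---|---|
| Lead-in effect retained (c = 0) | −0.40, z = 2.76 | about 78%, favours TNX/TNX | −0.16, z = 1.24 | about 24%, favours TNX/TNX |
| Half catch-up (c = 0.2) | −0.20, z = 1.38 | about 28%, favours TNX/TNX | +0.04, z = 0.31 | about 6% |
| Full catch-up (c = 0.4) | 0 | about 5% | +0.24, z = 1.86 | about 46%, favours former placebo |
| Equal gains, no lead-in difference (d = c = 0) | 0 | about 5% | 0 | about 5% |

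Because g cancels, the first row is the same whether the drug adds nothing in the extension or helps both arms equally.

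Over n = 40 to 120 and d = 0.3 to 0.5 SD, the retained effect is significant from the P301 baseline in about 30% (n = 40, 0.3 SD) to 99% (n = 120, 0.5 SD). Full catch-up gives a significant P303-baseline result for former placebo in about 16% to 81%.

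**4. Second set of assumptions.** d = 5 CAPS-5 points; SD 12 at both later times and 8 at the P301 baseline; correlation 0.5 to 0.9 between the two later scores; 50 or 100 per arm.

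- Retained effect: P301 contrast −5, significant in 62–90%; P303 contrast −0.5 to −2.5, significant in 7–36%.
- Half catch-up: P301 contrast −2.5, significant in 20–35%; P303 contrast 0 to +2.0, significant for former placebo in 2–74%.
- Full catch-up: P301 contrast 0; P303 contrast +2.5 to +4.5, significant for former placebo in 22–100%.

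**5. Comparison.** A one-sample test of P303-baseline change in Placebo/TNX, which the SAP does not plan, follows extension change. Under the assumptions of step 4 it is significant in 83–100% with full catch-up, and at about the nominal 5% when only the lead-in effect exists. It cannot separate drug from time, expectancy or co-medication.

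**The case against.** **The SAP is open about the contrast, and its inferential claims are modest.** SAP 3.2 and 9.1.1 name the contrast. P-values are nominal (SAP 7.1.1.1), there is no formal testing order (SAP 7.2), and no success rule exists. Safety is the primary objective. Efficacy change is already summarised descriptively by former arm and overall. All of this stands and limits the impact; it does not make the tests answer Protocol 5.2.

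**The labels attach to endpoints.** *Primary* and *key secondary* sit in text that refers to Visit 6 and to randomisation, which does not fit a five-visit study without randomisation. That may be a clean-up matter. Still, the only test planned for those endpoints is the former-arm one.

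**The alternative is weaker in one respect.** Within-arm change has no control, and Protocol 8.5 relaxes co-medication limits. The former-arm contrast at least derives from randomisation, though among selected lead-in completers. This is why the within-arm estimate should be called uncontrolled.

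**Stronger readings a reader might infer.**

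- *That a working drug must give a null or reversed result, and a lead-in effect must give a significant one.* Neither follows. The outcome depends on the baseline, the degree of catch-up and N, as the half catch-up and n = 40 results show.
- *That 78% against 5% is type I error inflation.* It is not: the former arms truly differ from the P301 baseline in that scenario.
- *That the SAP made an undeclared change.* This is only arguable. Protocol 12.5 names CAPS-5 but does not exclude other endpoints, and Protocol 6.3.2 announces testing on all of them for two defined groups, so between-group tests are a reasonable reading.

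**Conclusion.** The point holds on the text: no planned efficacy p-value tests efficacy over the additional 12 weeks. The direction of possible misreading follows from the algebra. A retained lead-in effect can make the P301-baseline result significant, and full catch-up makes it null and can reverse the P303-baseline result. Short of full catch-up the effects are milder. The percentages rest on assumed N, effect sizes, SDs and correlations, with no dropout and without the site, sex, tobacco and MDE covariates of SAP 9.1.1; they show scale and are not predictions. With nominal p-values and a safety primary objective, this is a change that should be made to labelling and interpretation. It does not threaten the study's main purpose.

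**What to change.** 1. In SAP 7.2.1, 7.2.2, 9.1.1 and 9.1.2, label the former-arm tests as exploratory comparisons of early versus delayed start among lead-in completers, state that they do not test efficacy in the extension, and remove *primary* and *key secondary* from them.
2. State how each contrast reads. The P301-baseline difference includes the lead-in effect, and a value near zero is what full catch-up would produce. On the P303 baseline, greater improvement in Placebo/TNX is the direction expected if switchers catch up. The ANCOVA there adjusts for a post-randomisation value and so carries an offset of (1 − b)d towards TNX/TNX.
3. Base the efficacy statement on estimated change from the P303 baseline by former arm, chiefly Placebo/TNX (first exposure), with 95% CIs. Describe it as uncontrolled and open to time, expectancy and relaxed co-medication effects.
4. For consistency, list in SAP 12 that the former-arm comparison covers endpoints beyond the CAPS-5 comparison named in Protocol 12.5.

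Cost: SAP wording, table titles and by-arm estimates from data already planned; no new data. The downside is that fewer p-values carry an efficacy label and the efficacy statement is openly uncontrolled.

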10.2.5. Beck Depression Index (BDI-II)

BDI-II refers to the patient-rated assessments of depressive symptomology. The BDI-II will be administered at Baseline (Visit 1) and Visits 3, 4, and endpoint (Visit 5).

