in separate, independent models. The model will include all participants in the safety population, and the dependent variable will be the observed change from each baseline at each post-randomization visit. Covariates in the model will include the fixed categorical effects of treatment, site, sex, current tobacco use status, presence of current MDE, visit and treatment by visit interaction, as well as the continuous fixed covariates of baseline score and baseline score by visit interaction. An unstructured covariance matrix will be used to model the within-subject variance-covariance errors. The Kenward-Roger approximation will be used to estimate the denominator degrees of freedom. Should the unstructured model fail to converge, an autoregressive AR(1) covariance structure will be attempted, then finally compound symmetric should AR(1) not converge.

The least squares means and 95% confidence intervals (CIs) will be calculated for the treatment difference between the subjects that received TNX-102 SL and placebo in the lead-in study at each time point.

CGI-I score (which does not have baseline assessments) will use the same method, however, the observed baseline response and associated interactions removed from the list of covariates. All visits will be included in the analysis. P-values from these comparisons will be considered nominal.

For each outcome, descriptive statistics (mean, SD, median, minimum and maximum) will be reported as well as LS means, standard error (SE) and p-values comparing the arms at each visit. In addition, for the SDS, the frequency of participants not working or attending school due to reasons unrelated to PTSD will be reported overall and within each visit.

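### If the unstructured MMRM fails to converge, the SAP's fallback forces one variance on Weeks 4, 8 and 12, which miscalibrates by-visit intervals when spread differs by visit, mainly for BDI-II change from the P303 baseline

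*SAP*

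**What the plan says.** SAP 9.1.1 fits a repeated-measures model to BDI-II, separately for the P301 and P303 baselines; "the dependent variable will be the observed change from each baseline at each post-randomization visit". Protocol 10.2.5 collects BDI-II after baseline at Visits 3, 4 and 5, that is, Weeks 4, 8 and 12. Nobody is randomized in P303, so I read the visits in the model as these three.

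On covariance: "An unstructured covariance matrix will be used to model the within-subject variance-covariance errors". On inference: "The Kenward-Roger approximation will be used to estimate the denominator degrees of freedom". If the fit fails: "Should the unstructured model fail to converge, an autoregressive AR(1) covariance structure will be attempted, then finally compound symmetric should AR(1) not converge". No heterogeneous structure and no sandwich variance is named in either document.

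The rule also covers a second endpoint: "CGI-I score (which does not have baseline assessments) will use the same method", without the baseline terms. The same section asks for LS mean differences between the lead-in arms, with 95% intervals and p-values, at each visit. CAPS-5, SDS and PROMIS go to a single-time-point ANCOVA instead.

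**The concern.** An unstructured matrix lets each visit have its own variance. AR(1) and compound symmetry, as named, have one variance for all visits. The fallback therefore simplifies the correlations and also discards the visit-specific variances. A contrast at one visit depends directly on that visit's variance, so a pooled value gives the wrong standard error wherever the spread departs from the average. Kenward-Roger is a small-sample adjustment that takes the fitted structure as correct.

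The outcome is change from baseline, adjusted for baseline. If a score's correlation with baseline weakens with time, the residual variance rises from visit to visit. The Week 12 interval would then be too narrow and the Week 4 interval too wide. BDI-II is listed as both an efficacy and a safety endpoint (SAP 2.2.1 and 2.2.2), so its Week 12 interval will be read.

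**Working it through.** The documents state no SD, correlation or sample size, so there is no plan figure to reproduce. All SDs, correlations, dropout rates and sample sizes below are assumptions.

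**Step 1: closed form, complete data.** A common-variance structure uses approximately

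pooled SD = sqrt(mean of the three visit variances)

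The ratio of reported to true standard error at visit j is r = pooled SD / SD_j, and the type I error is 2(1 − Φ(1.96 r)). For example, with 8/9/10 the pooled SD is sqrt((64 + 81 + 100)/3) = 9.04. At Week 12, r = 9.04/10 = 0.904 and the error is 7.7%.

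| Assumed SDs, Weeks 4/8/12 | Pooled SD | Week 4: r, error | Week 12: r, error |
|---|---|---|---|
| 9/9/9 | 9.00 | 1.00, 5.0% | 1.00, 5.0% |
| 8/9/10 | 9.04 | 1.13, 2.7% | 0.904, 7.7% |
| 7/9/11 | 9.15 | 1.31, 1.0% | 0.832, 10.3% |
| 6/9/12 | 9.33 | 1.56, 0.2% | 0.777, 12.8% |
| 11/9/7 (shrinking) | 9.15 | 0.832, 10.3% | 1.31, 1.0% |

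**Step 2: which baseline matters.** Take a scale with constant raw SD and correlation ρ per 4 weeks. The residual variance after baseline adjustment is then proportional to 1 − ρ^(2 × lag). In 4-week units the lags are 1, 2, 3 from the P303 baseline and 4, 5, 6 from the P301 baseline, which lies 12 weeks earlier. For ρ = 0.9 and P303 the variances are 0.190, 0.344 and 0.469, with mean 0.334, so r at Week 12 = sqrt(0.334/0.469) = 0.844.

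| ρ | P303 baseline: r, Week 12 error | P301 baseline: r, Week 12 error |
|---|---|---|
| 0.9 | 0.844, 9.8% | 0.949, 6.3% |
| 0.8 | 0.873, 8.7% | 0.975, 5.6% |
| 0.7 | 0.902, 7.7% | 0.990, 5.2% |

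**Step 3: REML simulation.** The setting was N = 150, lag-one correlation 0.7, about 20% dropout and model-based standard errors. Week 12 coverage of a nominal 95% interval was:

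- SDs 7/9/11, 1000 runs: unstructured 95.7%, AR(1) 89.9%, compound symmetry 89.6%. Mean standard errors were 1.94, 1.58 and 1.57.
- Equal SDs, 600 runs: 94.7%, 95.0% and 94.7%.

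This agrees with the closed form (89.7% and 95.0%). A second simulation (80 per arm, 8% dropout per interval, 400 runs) gave a Week 12 error of 5.0% with heterogeneous AR(1), for both 8/9/10 and 7/9/11. Its Monte Carlo standard error is about sqrt(0.05 × 0.95/400) = 1.1 points.

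**Step 4: parameter counts with three visits.**

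- Unstructured: 3 variances + 3 covariances = 6.
- AR(1) or compound symmetry: 1 + 1 = 2.
- Heterogeneous AR(1) or compound symmetry: 3 + 1 = 4.
- Heterogeneous Toeplitz: 3 + 2 = 5.

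**The case against.** The best counter-argument is that the fallback will hardly ever run. Six covariance parameters over three visits are easy to estimate. In a check with the SAP's covariates, SDs 7/9/11 and 8% dropout per interval, the unstructured fit converged in 100 of 100 runs in each of four settings (N = 160 or 80, with 1 or 35 sites). That check used a Cholesky parameterisation outside SAS, and 100 runs cannot exclude rare failures, but the point stands.

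A reader might infer that about 35 sites, or the absence of a planned sample size, make failure more likely. The documents do not support this. Site enters as a fixed main effect and adds no covariance parameters, and an unplanned sample size is not necessarily a small one.

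A reader might also infer that Week 12 results would be wrong for both endpoints and both baselines. That goes too far:

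- Step 2 leaves little error for the P301 baseline.
- CGI-I is a bounded 1–7 rating with no baseline covariate, so the spreading-change mechanism does not carry over, and no calculation shows an effect for it.
- With equal SDs there is no error even when the fallback is used.

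Finally, the stakes are modest. The primary objective is safety, p-values are nominal (SAP 7.1.1.1), and by-visit SDs will be tabulated anyway, so unequal spread would be visible. All this lowers the priority. It does not make the common-variance fallback a sound choice.

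**Conclusion.** The point holds as a conditional defect of low priority. If the unstructured fit fails and residual spread differs by visit, the by-visit standard errors, intervals and p-values from the stated fallback are miscalibrated. Under growing spread the Week 12 type I error is about 7.7% (assumed SDs 8/9/10) to 10.3% (7/9/11); shrinking spread reverses the direction. The actual size in this trial cannot be determined from the documents.

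The case is plausible mainly for BDI-II change from the P303 baseline, where Step 2 gives 7.7–9.8%. For the P301 baseline it gives 5.2–6.3%. The rule applies to CGI-I, but no effect is shown there. CAPS-5, SDS and PROMIS are untouched.

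These percentages should not be read as error rates of the SAP's whole procedure. They come from applying the fallback to all generated datasets, not to those where the unstructured fit failed. If failure had probability 3% (an assumption) and failing datasets were like the rest, the overall rate with 7/9/11 would be 0.97 × 5.0% + 0.03 × 10.3% = 5.2%.

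**What to change.** Replace the fallback sentence in SAP 9.1.1 with this order:

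1. Refit the unstructured model with a Cholesky parameterisation and alternative starting values.
2. If that fails, use heterogeneous AR(1).
3. If that fails, use heterogeneous compound symmetry.

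Keep REML and Kenward-Roger at every step. The primary model is unchanged and no new data are needed. Settling this before database lock also avoids a post-hoc choice of structure.

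The cost is one sentence and two more variance parameters than the current fallback (4 against 2). Heterogeneous Toeplitz could be placed before step 2, but it is optional: at 5 parameters it has three more than the current fallback and only one fewer than unstructured, so it offers little relief when the unstructured fit has failed.

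### The CGI-I model has no baseline severity covariate and the responder tests stratify only by current MDE, although CAPS-5 at the P301 baseline is available for both

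*SAP*

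**What the plan says.** **Continuous endpoints (SAP 9.1.1).** Endpoints measured at baseline and Week 12 are analysed by ANCOVA, and BDI-II by MMRM. Both models include the patient's own baseline score, and the MMRM adds its interaction with visit. The categorical terms of the MMRM are "treatment, site, sex, current tobacco use status, presence of current MDE, visit and treatment by visit interaction".

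**CGI-I (SAP 9.1.1).** The SAP states that "CGI-I score (which does not have baseline assessments) will use the same method", with "the observed baseline response and associated interactions removed from the list of covariates". Two terms therefore leave the model: baseline score and baseline score by visit. Four baseline covariates stay: site, sex, tobacco use and current MDE. No other severity measure is put in.

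**Responder endpoints (SAP 9.1.2).** There are two: a CGI-I rating of much or very much improved, and at least 50% "improvement from baseline in Total CAPS-5 score". Both are tested by a "Cochran Mantel Haenszel (CMH) test stratified by presence of current major depressive episode". Missing data count as non-response. Risk differences with 95% CIs are reported.

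**What is available.** SAP 2.2.1 lists CAPS-5 change from both baselines, so CAPS-5 total is held at each. SAP 7.1 places the P301 baseline before the first double-blind dose. The P303 value comes from the final lead-in visit (Protocol 10.2.1 and 12), which follows 12 weeks of randomised treatment.

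**Who is compared.** The groups are the lead-in arms, and everyone takes active drug in P303 (SAP 3.2). Under Protocol 7.2, entrants completed the lead-in, were at least 60% compliant, had no significant worsening of depression or clinically significant rise in suicidal ideation, and consented.

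**The concern.** The SAP adjusts the other continuous endpoints for baseline level. The lack of a baseline rating for CGI-I explains why that term is removed, but not why severity is left out. CGI-I rates change from each of two baselines (Protocol 10.2.2), so severity at baseline is a natural covariate. The responder tests raise the same question. Change in CAPS-5 total is adjusted for baseline CAPS-5, site, sex, tobacco use and MDE, whereas the 50% responder version of the same score is adjusted for MDE only, and no reason is given.

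Two things are at stake. If baseline severity predicts outcome, leaving it out of the CGI-I model gives wider intervals than the data allow. And because entry to P303 depends on events after randomisation that may differ by arm, the lead-in arms may differ in severity. The planned analyses would correct such a difference only as far as the retained covariates carry it.

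**Working it through.** **No plan figure to reproduce.** The documents give no sample size, power, effect size, SD or correlation for these endpoints (Protocol 12.3, SAP 5). Every input below is an assumption, shown as a range.

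**1. CGI-I, continuous.** Let ρ be the correlation of baseline CAPS-5 with CGI-I, given the covariates already in the model. Let d be the arm imbalance in CAPS-5, in SD units, that those covariates leave. With the linear-model approximation at a single visit:

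- SE ratio, adjusted to unadjusted = √(1 − ρ²)
- Extra patients equivalent to not adjusting = 1/(1 − ρ²) − 1
- Bias left by imbalance = ρ × d, in outcome SDs

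| ρ | SE ratio | SE reduction | Equivalent extra patients | Bias at d = 0.2 |
|---|---|---|---|---|
| 0.1 | √0.99 = 0.995 | 0.5% | 1.0% | 0.02 SD |
| 0.3 | √0.91 = 0.954 | about 5% | 9.9% | 0.06 SD |
| 0.5 | √0.75 = 0.866 | about 13% | 33.3% | 0.10 SD |

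In scale units, take ρ = 0.3, CGI-I SD 1.2 and CAPS-5 SD 8, all assumed. The slope is 0.3 × 1.2 / 8 = 0.045 CGI-I units per CAPS-5 point. A 2-point arm imbalance then moves the contrast by 2 × 0.045 = 0.09 on the 1–7 scale.

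**2. Responder endpoints.** The formula in step 1 is for linear models, so this part was simulated. The settings were 100 patients per arm, about 50% response, no true effect, 3,000 runs per setting, and MDE moderately related to severity (latent correlation 0.3). The Mantel-Haenszel risk difference stratified by MDE only was compared with one stratified by MDE and CAPS-5 tertile.

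| ρ | SD of estimate, no imbalance: MDE only | MDE + tertile | Spurious difference, d = 0.2: MDE only | MDE + tertile |
|---|---|---|---|---|
| 0.1 | 0.0716 | 0.0722 | 0.5 points | about 0.0 |
| 0.3 | 0.0701 | 0.0696 | 2.2 points | 0.4 |
| 0.5 | 0.0700 | 0.0665 | 3.9 points | 0.8 |

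Simulation error on each mean is about 0.07/√3000 = 0.0013, or 0.13 percentage points. Precision changes by under 1% at ρ = 0.1 and 0.3. It improves by about 5% (0.0665/0.0700 = 0.95) only at ρ = 0.5. The clearer effect is on bias.

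**3. Which baseline.** P301 CAPS-5 precedes randomised treatment, so adjusting for it cannot remove any of the lead-in treatment effect. P303-baseline CAPS-5 follows 12 weeks of that treatment. Conditioning on it can absorb part of the lead-in effect, so the contrast becomes one between arms at equal severity on entry to P303. That is a different question.

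**The case against.** A reader might infer that the CGI-I model drops all baseline adjustment and has no protection against imbalance. The text does not support that. Only the baseline response and its interactions go, while site, sex, tobacco use and MDE stay. The responder tests also keep MDE as a stratum.

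A reader might also take precision loss and arm imbalance as established. Neither is. The documents give no correlation and no observed imbalance. CGI-I is itself a rating of change, and the CAPS-5 responder is defined as a percentage of the patient's own baseline, so nothing in the documents shows that baseline severity predicts either. The relevant correlation is the one left after the retained covariates, which may be small. For the responder tests, a general claim of wider intervals fails at ρ = 0.1 and 0.3.

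The stakes can be overstated too. SAP 7.2.2 says that CGI-I status since the start of treatment "is the first key secondary efficacy endpoint in this study", but the same paragraph speaks of participants being randomised and of treatment starting at Visit 2. Neither fits P303, where nobody is randomised and Visit 2 is a telephone call. SAP 7.2 sets no formal testing order, and SAP 7.1.1.1 makes all p-values nominal. Protocol 12.5 lists the lead-in-arm comparison as exploratory and names only CAPS-5, although Protocol 6.3.2 does promise hypothesis tests on all the efficacy endpoints.

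All of this stands and limits the size of the point. An MDE-stratified CMH test is valid, and adjusting for one measured variable cannot undo selection through completion, compliance and consent. What remains is that a plausible severity covariate, already collected, is left out of these analyses without a stated reason, in a comparison that randomisation no longer fully protects.

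**Conclusion.** The gap is real but limited. The CGI-I MMRM has no baseline symptom-severity covariate, and the two responder tests adjust for current MDE alone, although CAPS-5 total at the P301 baseline is available.

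- For CGI-I, adding it would reduce the SE by about 0.5%, 5% or 13% at assumed partial correlations of 0.1, 0.3 or 0.5. It would also remove a bias of 0.02, 0.06 or 0.10 SD if the arms differ by 0.2 SD.
- For the responder endpoints, the gain is mainly protection against a spurious difference of about 0.5 to 4 percentage points under the same assumed imbalance. Precision hardly changes unless the correlation is near 0.5.

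These are illustrations, since neither the correlation nor any imbalance is documented. Impact is low to moderate: no type I error claim rests on these tests and the primary objective is safety. The change is worth making because it costs almost nothing, and because fixing the covariate in advance avoids choosing it after an imbalance has been seen.

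**What to change.** 1. **CGI-I MMRM (SAP 9.1.1).** Replace the removed baseline term with P301-baseline CAPS-5 total and its interaction with visit. If P303-baseline CAPS-5 is used instead for CGI-I rated from the P303 baseline, to match the other P303-baseline models, state that it is measured after randomised treatment and changes the question.
2. **Responder endpoints (SAP 9.1.2).** Keep the CMH analysis. Alongside it, add a supportive logistic model with lead-in arm, P301-baseline CAPS-5, current MDE, sex and tobacco use. Report the standardised risk difference with its 95% CI. Keep missing as non-response, so that the two analyses differ only in covariates. Name P301 as the covariate baseline for responder status defined from either baseline.
3. **Interpretation.** State that adjustment addresses measured severity only and does not restore the balance of the lead-in randomisation.

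The cost is a few sentences in the SAP and a few lines of code, with no new data. It should be settled before database lock. If the lock has passed, SAP 4.1 already requires such an analysis to be reported as post hoc.
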